## 8.1 Screening

All subjects will be screened for study eligibility. All subjects must sign informed consent prior to any screening procedures being performed.

Activities for screening will begin up to 30 days prior to initiation of study treatment with eltrombopag. During this time, all subjects will complete a bone marrow aspirate and biopsy to confirm current SAA status. The eligibility criteria is found in [Section 5](#).

Information regarding eligibility criteria will be collected on the Inclusion/Exclusion eCRF. Subjects who do not meet all entry criteria should not be entered into the study.

Re-screening is not allowed in this study. In the case where a safety laboratory assessment at screening is outside of the range specified in the exclusion criteria, the assessment may be repeated once prior to initiation of study treatment. If the repeat value remains outside of the specified ranges, the subject must be excluded from the study.

### 8.1.1 Information to be collected on screening failures

Subjects who sign an informed consent form and subsequently found to be ineligible will be considered a screen failure. The reason for screen failure should be entered on the applicable Case Report Form. The demographic information, informed consent, and Inclusion/Exclusion pages must also be completed for screen failure subjects. No other data will be entered into the clinical database for subjects who are screen failures, unless the subject experienced a serious adverse event during the screening phase (see SAE section for reporting details). Subjects who sign an informed consent and are considered eligible but fail to be started on treatment for any reason will be considered an early terminator. The reason for early termination should be captured on the appropriate disposition Case Report Form.

## 8.2 Subject demographics/other baseline characteristics

Subject demographic and baseline characteristic data to be assessed on all subjects include:

- Demographic information: Age, gender, height and weight, body temperature, BP and pulse measurements
- Date of diagnosis, etc. of aplastic anemia
- Prior treatment for AA including transfusion history, and concomitant medications (see [Section 6.2.1](#))
- Laboratory evaluations: ECG, Peripheral blood smear, Bone marrow aspiration (iliac crest) and cytogenetic analysis, Bone marrow biopsy, Hematology and Chemistry test, Blood coagulation test, Pregnancy test, Hepatitis and HIV Screen, Plasma thrombopoietin, and Flow Cytometry of the Peripheral Blood for glycosylphosphatidylinositol (GPI)-cells.
- Medical history (all important medical, surgical, and allergic conditions that could have an impact on the subject's evaluation) / current medical conditions (e.g. all relevant current medical conditions which are present at the time of signing informed consent). Ongoing medical conditions, symptoms and diseases which are recorded on the Medical History eCRF should include the toxicity grade when applicable.

Investigators will have the discretion to record abnormal test findings on the medical history CRF whenever in their judgment, the test abnormality occurred prior to the informed consent signature.

## 8.3 Efficacy

### 8.3.1 Primary endpoint

Primary Endpoint - hematologic response rate at Week 26 (6 months) defined as the proportion of all subjects who meet any of the IWG criteria shown in the table below. Hematologic response assessment will be performed by investigators.

**Table 8-2 IWG criteria for Primary Endpoint**

Assessment Item	Baseline transfusion status	Response Criteria
Platelet count	Platelet transfusion independent	Transfusion independent and increase from baseline by $20 \times 10^9/L$ or more
	Platelet transfusion dependent	No platelet transfusion requirement for 8 weeks
Hemoglobin	RBC transfusion independent	When the baseline hemoglobin level is < 90 g/L: transfusion independent and increase from baseline by 15 g/L or more
	RBC transfusion dependent	A decrease of at least 4 units in RBC transfusions in the post-treatment 8-week period (1 unit = RBC derived from 200 mL blood) Or no RBC transfusion requirement for 8 weeks (less than 4 units RBC in 8-week period at Baseline)
Neutrophil count	NA	(In the absence of G-CSF taken within 21 days preceding the blood sample collection) Increase from baseline by $0.5 \times 10^9/L$ or more, or (if < $0.5 \times 10^9/L$ at baseline) increase by 100% or more

**During regular hematologic assessment, the exclusion period of transfusion and G-CSF are detailed below:**

Platelet transfusion: 7 days preceding the assessment of platelet count

RBC transfusion: 14 days preceding the assessment of hemoglobin

G-CSF: 21 days preceding the assessment of neutrophil count

### Definition of baseline Platelet Transfusion Independence/Dependence and platelet count

Baseline platelet transfusion independence/dependence and platelet count are defined as:

- For platelet transfusion independent subjects that did not receive platelet transfusions in the 4 weeks before Day 1: The average of the most recent 2 platelet counts before Day 1.
- For transfusion dependent subjects that received one or more platelet transfusions in the 4 weeks before Day 1: The average of the most recent 2 platelet counts before Day 1

(excluding platelet counts within 6 days \* following a platelet transfusion). If all platelet counts available are within 6 days\* following a platelet transfusion, the lowest platelet count prior to initiation of study drug will be used as the baseline platelet count.

\*: e.g. When a platelet transfusion was done on December 2nd (Monday), the platelet count will become available for on December 9th (Monday).

#### **Definition of baseline RBC Transfusion Independence/Dependence and hemoglobin value**

Baseline RBC transfusion independence/dependence and hemoglobin value are defined as:

- For RBC transfusion independent subjects that did not receive RBC transfusions in the 8 weeks before Day 1: The most recent hemoglobin value before Day1.
- For RBC transfusion dependent subjects that received one or more RBC transfusions in the 8 weeks before Day 1: The last hemoglobin value prior to the most recent RBC transfusion. If no values exist prior to a RBC transfusion, the lowest value before Day1 will be used.

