##### **Supportive therapy**

Supportive therapy can be used if clinically required.

- Transfusion (RBC and platelets) and G-CSF is performed as the following guide:

RBC transfusion: Keep the hemoglobin concentration at over 60 g/L or in the presence of clinical symptoms such as dyspnea.

Platelet transfusion: The platelet count is less than  $10 \times 10^9/L$  or when significant bleeding occurs.

G-CSF: The neutrophil count is less than  $0.2 \times 10^9/L$ .

- Iron chelation therapy: Start of this drug is not allowed until Week 26 efficacy assessment. If using before the start of the investigational drug, continued usage is allowed.

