#### **8.4.1 Laboratory evaluations**

Clinically significant abnormalities must be recorded as either medical history or adverse events as appropriate.

All laboratory tests are performed at the study site or designated lab. Examinations at the point of the start of the investigational product must be performed before the starting of dosing. The hematology test must be conduct before the supportive therapy (if supportive therapy is performed).

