2.7.2 Statistical hypothesis, model, and method of analysis

Hematological Response at Week 13 and Week 52

The number and percentage of subjects who meet the hematological response criteria (at Week 13 and Week 52 respectively) will be presented and exact 90% confidence interval will be reported. And the number and percentage of assessment item for the hematological response criteria and for the detailed hematological response criteria will be presented.

The derived response by programming at week 13 and Week 52 will also be summarized as above.

Changes in platelet count, hemoglobin and neutrophil count

Values and changes in platelet count (in the absence of platelet transfusion), hemoglobin (in the absence of RBC transfusion) and neutrophil count (in the absence of G-CSF) will be summarized at each visit. Descriptive statistics including mean, SD, median, 25th and 75th percentiles, minimum, and maximum will be summarized for the changes.

Median and interquartile range will be plotted.

Time to hematological response

The distribution function of time to hematologic response will be estimated using the Kaplan-Meier method and will be plotted. The median time to hematologic response along with 90% CIs will be presented. If a subject does not meet hematological response before or at the cutoff date, censoring will be performed using the date of the last assessment.

Duration of hematological response

The distribution function of duration of hematologic response will be estimated using the Kaplan-Meier method and will be plotted. If the number of relapses or deaths allows, the median time to hematologic response along with 90% CIs will be presented.

Relapse-free probability will be estimated using the Kaplan-Meier method at 3 months, 6 months, 9 monthes, one year, and yearly after as well.

Frequency and amount of transfusion

The frequency and the amount of platelets transfusion in each period (Baseline: 4 weeks before Day 1; Week 13, 26, 52: 4 weeks before each visit day) will be summarized by descriptive statistics including mean, SD, median, 25th and 75th percentiles, minimum, and maximum.

Proportion of subjects with transfusion decrease

The number and percentage of subjects with platelet or RBC transfusion decrease or transfusion-free in each period will be presented.

In addition, the number and percentage of subjects with 50% platelet or RBC transfusion reduction in each period will be presented.

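### Change in hemoglobin is not like-for-like in RBC-transfusion-dependent subjects: a pre-transfusion baseline is set against follow-up values that need only be 14 days clear of a transfusion, and the SAP does not say which baseline applies

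*Protocol*

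**What the plan says.** Protocol 8.3.1 classes a subject with one or more RBC transfusions in the 8 weeks before Day 1 as RBC-transfusion-dependent. Baseline hemoglobin is then "The last hemoglobin value prior to the most recent RBC transfusion". The fallback reads: "If no values exist prior to a RBC transfusion, the lowest value before Day1 will be used". SAP 2.5.1 repeats both rules and adds only that Day 1 counts.

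For follow-up, the same sections give one exclusion window: "RBC transfusion: 14 days preceding the assessment of hemoglobin". Nothing requires a follow-up value to be a pre-transfusion value.

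Change in hemoglobin is a secondary endpoint (Protocol Table 2-1, SAP 1.2). SAP 2.7.2 states that "hemoglobin (in the absence of RBC transfusion) and neutrophil count (in the absence of G-CSF) will be summarized at each visit", with plots of median and interquartile range. SAP 2.7.1 keeps it among the few efficacy analyses to be produced for the final report. Neither section names a baseline. SAP 2.1.3 separately defines baseline, for safety and efficacy alike, as the last assessment on or before first dose.

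Two other provisions matter. Protocol 6.2.1.1 guides transfusion as follows: "RBC transfusion: Keep the hemoglobin concentration at over 60 g/L or in the presence of clinical symptoms such as dyspnea". Protocol 8.4.1 orders tests and support: "The hematology test must be conduct before the supportive therapy".

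For platelets, Protocol 8.3.1 averages the two most recent counts, for transfusion-dependent subjects "excluding platelet counts within 6 days" of a transfusion. That nearly matches the 7-day follow-up window, although the platelet rule also falls back to a lowest value.

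**The concern.** Hemoglobin in a regularly transfused subject follows a saw-tooth: up after each transfusion, then down to the level at which the next is given. The transfusion-specific baseline takes the bottom of that cycle. The follow-up window accepts any point from day 14 of the cycle onward. Even if transfusion need never changes, the average follow-up value then sits above baseline. Measurement error adds to this, because a value that prompts a transfusion tends to be low partly by chance.

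What is at stake is a descriptive secondary endpoint, reported at every visit and again in the final report. The trial has one arm and rests on estimation, so no control group would show how much of the rise comes from the definitions. The summary of hemoglobin regardless of transfusion (Protocol 12.5.2) does not help, because it admits values soon after a transfusion.

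**Working it through.** **The plan's own figure.** The documents give none for hemoglobin change. The one design calculation, the exact 90% interval with n = 20, recomputes as printed: for 4, 6, 8 and 10 responders, (7.1, 40.1), (14.0, 50.8), (21.7, 60.6) and (30.2, 69.8). It does not depend on this point.

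**Inputs from the documents.** The two baseline rules, the 14-day window, and the test-before-transfusion order, as cited above.

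**Assumed inputs.** Each transfusion raises hemoglobin by R g/L. It falls linearly back to the trough over T days. Need is stable, there is no drug effect, and eligible follow-up values fall uniformly over days 14 to T of the cycle. The documents give neither R nor T, so a range is shown.

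**Formula.** At t days after a transfusion, hemoglobin stands R(1 - t/T) above the trough. The mean over days 14 to T is R(T - 14)/(2T).

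- Transfusion-specific baseline (height 0): expected change = R(T - 14)/(2T). With R = 20 and T = 28: 20 x 14/56 = +5.0 g/L.
- General baseline, a random point in the cycle (mean height R/2): expected change = R(T - 14)/(2T) - R/2 = -7R/T. With R = 20 and T = 28: -140/28 = -5.0 g/L.

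No-effect mean change, g/L:

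| T (days) | Specific, R = 10 | Specific, R = 20 | General, R = 10 | General, R = 20 |
|---|---|---|---|---|
| 21 | +1.67 | +3.33 | -3.33 | -6.67 |
| 28 | +2.50 | +5.00 | -2.50 | -5.00 |
| 42 | +3.33 | +6.67 | -1.67 | -3.33 |
| 56 | +3.75 | +7.50 | -1.25 | -2.50 |

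At T of 14 days or less almost no follow-up value is eligible.

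**Simulation with the transfusion-specific baseline** (trigger 60 g/L, R of 10 and 20, T of 21 to 42 days):

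- Hemoglobin checked about every 4 days, visits every 14 or 28 days: +1.8 to +7.0 g/L without measurement error, and +4.4 to +9.9 g/L with an assumed SD of 3 g/L.
- Tests and transfusions only at visits every 14 days, test first, SD 3: +1.9 to +7.5 g/L. The rise is smaller than with between-visit checks (+4.8 to +9.9 on the same visit grid), but it does not vanish, because some eligible visits are not followed by a transfusion.

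**Same rule on both sides.** If baseline and follow-up both come from values at least 14 days after a transfusion, the closed-form change is 0. In simulation it is -0.8 to +0.7 g/L when baseline values come from the same visit grid as follow-up. When any between-visit check could serve as baseline, +2.2 to +4.2 g/L remained with SD 3, so the type of visit should match too. Using only pre-transfusion values on both sides also gives an expected change of 0 in this model.

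**Cost of a mid-cycle baseline.** A baseline taken after day 14 stands R(T - 14)/(2T) above the trough. In a subject who becomes transfusion-free it would understate the gain by that amount, for example 5.0 g/L at R = 20 and T = 28.

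**The case against.** The strongest objection is that the SAP never assigns the transfusion-specific baseline to this endpoint. It stands in the section on response criteria, while SAP 2.1.3 claims efficacy evaluations generally, and under that definition the sign reverses. This stands. A reader might infer that hemoglobin change must rise without a drug effect, but the documents support that only conditionally. Nor do they show that this endpoint is the baseline's only use, although RBC-dependent subjects are judged on units in Table 8-2 and not on hemoglobin change.

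The follow-up rule is also partly inferred. No sentence ties the 14-day window to the endpoint's condition that RBC transfusion be absent. It is, however, the only operational rule given.

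Some further inferences go too far:

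- A reader might take baseline to be about 60 g/L. The guide allows transfusion for symptoms, it is on-study guidance, and the last earlier value may be days old.
- A subject transfused once around Day -50 might seem to keep a much older low value. Screening starts at Day -30 (Protocol 8.1), and the documents do not show that hemoglobin from before such a transfusion is collected.
- One might expect the largest distortion in the most heavily transfused subjects. The formula says the opposite: the rise is smallest at short intervals.

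Finally, a pre-transfusion value is a defensible baseline, being the least affected by transfusion. That is so, but it then needs pre-transfusion values at follow-up for subjects still transfused. Test-before-transfusion makes some follow-up values troughs, but not all.

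**Conclusion.** The point holds in conditional form. With the baseline of Protocol 8.3.1 and SAP 2.5.1, the no-effect change in hemoglobin in RBC-dependent subjects with stable need is at or above zero: about +1.7 to +7.5 g/L for R of 10 to 20 g/L and T of 3 to 8 weeks. It approaches zero as follow-up values become pre-transfusion values. With the baseline of SAP 2.1.3 it is negative, about -2.5 to -5.0 g/L at T of 4 weeks. Neither reading is like-for-like. For scale, the response threshold in RBC-independent subjects is 15 g/L.

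The direction follows from the definitions under stable need. The size rests on assumed R, T, linear decline and measurement error.

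A reader might infer that the primary result is inflated. It is not: response in RBC-dependent subjects uses transfusion units or transfusion freedom, so the Week 26 rate, its interval and responder status are unaffected. The defect is confined to a descriptive secondary summary, but it is worth correcting because that summary is regenerated for the final report and has no control group.

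**What to change.** Change the SAP only, in 2.7.1 and 2.7.2:

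1. State which baseline applies to change in hemoglobin, and which follow-up values count as free of RBC transfusion.
2. Tabulate and plot RBC-dependent and RBC-independent subjects separately.
3. For RBC-dependent subjects still being transfused, apply one rule to both sides: either pre-transfusion values at baseline and follow-up, or values more than 14 days after a transfusion at both. Do not use the lowest-value fallback where an eligible value exists.
4. Keep the pre-transfusion baseline for subjects who have become transfusion-free, since a mid-cycle baseline would understate their gain.

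The first option in step 3 is simpler, because every RBC-dependent subject keeps the same baseline. The second makes the baseline depend on follow-up transfusion status, which the SAP would have to state openly.

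The cost is a small amount of reprogramming on data already collected. Relative to the transfusion-specific baseline, the reported hemoglobin change will be less favourable. Some continuity with the primary and updated analyses is lost, and a footnote in the final report should say so.

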#### **8.3.2 Secondary endpoints**

Hematologic response rate at Week 13 and Week 52 will also be assessed according to the response critieria for the primary endpoints by investigator.

Changes in platelet count, hemoglobin and neutrophil count will be calculated according to the lab test results entered into CRF.

Time to hematologic response and duration will be calculated for any response according to the response criteria for the primary endpoint.

Frequency and volume of transfusion of platelet and RBC will be required to recorded into CRF.

Clonal cytogenetic evolution will be evaluated during the study, and the rate of the subjects who developed any clonal evolution including clonal evolution to PNH, evolution to AML or MDS will be calculated..

#### **8.3.3 Appropriateness of efficacy assessments**

Since eltrombopag is expected to improve trilineage blood cells and decrease transfusion frequency based on the result from an overseas study in patients with SAA (ETB115AUS28T), this study uses the hematologic response rate, defined as the proportion of subjects showing improvement in at least one of the three blood cell lineages or a decrease in blood transfusion volume, as the primary endpoint as was the case in overseas studies.

### **8.4 Safety**

Safety assessments are specified below with the assessment schedule detailing when each assessment is to be performed.

For details on AE collection and reporting, refer to AE section.

**Table 8-3 Assessments & Specifications**

Assessment	Specification
Physical examination	
A complete physical examination will include the examination of general appearance, skin, neck (including thyroid), eyes, ears, nose, throat, lungs, heart, abdomen, back, lymph nodes, extremities, vascular, and neurological. If indicated based on medical history and/or symptoms, rectal, external genitalia, breast, and pelvic exams will be performed.
 
A short physical exam will include the examination of general appearance and vital signs (blood pressure [systolic blood pressure (SBP) and/or diastolic blood pressure (DBP)] and pulse). A short physical exam will be at all visits starting from week 1 except where a complete physical examination is required (see above).
 
Information for all physical examinations must be included in the source documentation at the study site. Clinically relevant findings that are present prior to signing informed consent must be included in the Medical History part of the CRF. Significant findings made after signing informed consent which meet the definition of an Adverse Event must be recorded on the Adverse Event section of the CRF.
 
ECOG Performance status scale will be used for screening and Day 1.

Vital sign	Vital signs include blood pressure (supine position preferred when ECG is collected), pulse measurement, and body temperature.
Height and weight	Height in centimeters (cm) and body weight (to the nearest 0.1 kilogram (kg) in indoor clothing, but without shoes) will be measured.

#### **8.4.1 Laboratory evaluations**

Clinically significant abnormalities must be recorded as either medical history or adverse events as appropriate.

All laboratory tests are performed at the study site or designated lab. Examinations at the point of the start of the investigational product must be performed before the starting of dosing. The hematology test must be conduct before the supportive therapy (if supportive therapy is performed).

**Table 8-4 Laboratory Assessments**

Test Category	Test Name
Hematology	Hematocrit, Hemoglobin, Platelets, Red blood cells, White blood cells, Differential (Basophils, Eosinophils, Lymphocytes, Monocytes, Neutrophils, Reticulocyte count, Bands, Other (absolute value preferred , percentages are acceptable)
Chemistry	Albumin, Alkaline phosphatase, ALT , AST , Lactate dehydrogenase (LDH), Calcium, Magnesium, Phosphorus, Sodium, Potassium, Creatinine, Direct Bilirubin, Total Bilirubin, Blood Urea Nitrogen (BUN) or Urea, Uric Acid Amylase, Lipase, Glucose (fasting)
Coagulation	Prothrombin time (PT) , International normalized ratio (INR), Activated partial thromboplastin time (aPTT)
Flow cytometry of the Peripheral Blood	Glycosylphosphatidylinositol (GPI)-cells
Hepatitis markers	HBsAg, HBsAb, HBcAb, HCV antibody

Test Category	Test Name
Additional tests	HIV antibody, plasma thrombopoietin
Pregnancy Test	Serum / Urine pregnancy test (refer to Pregnancy and assessments of fertility section)

#### 8.4.2    **Electrocardiogram (ECG)**

ECGs must be recorded after 10 minutes rest in the supine position to ensure a stable baseline. The preferred sequence of cardiovascular data collection during study visits is ECG collection first, followed by vital signs, and blood sampling. The Fridericia's QT correction formula (QTcF) should be used for clinical decisions.

The original ECGs and a certified copy on non-heat sensitive paper, appropriately signed, must be collected and archived at the study site. Each ECG tracing should be labeled with the study number, subject number, date, and kept in the source documents at the study site. Any identifier details must be redacted (e.g subject initials, date of birth). Interpretation of the tracing must be made by a qualified physician and documented on the relevant CRF pages.

For any ECGs with subject safety concerns, two additional ECGs must be performed to confirm the safety finding. A monitoring or review process should be in place for clinically significant ECG findings throughout the study and especially at baseline before administration of study treatment.

Clinically significant abnormalities must be recorded on the CRF as either medical history or adverse events as appropriate. Clinically significant findings must be discussed with Novartis prior to enrolling the subject in the study. New or worsened clinically significant findings occurring after informed consent must be recorded as adverse events.

Additional, unscheduled, safety ECGs may be repeated at the discretion of the investigator at any time during the study as clinically indicated. Unscheduled ECGs with clinically significant findings should be collected in triplicate. The individual ECGs should be recorded approximately 2 minutes apart. Local cardiologist ECG assessment may also be performed at any time during the study at the discretion of the investigator.

In the event that a QTcF value of > 500 ms is observed or if an unscheduled ECG is performed for safety reasons, it is recommended to collect a ECG time-matched PK sample as unscheduled PK sample and record the time and date of the last study drug intake to determine the drug exposure. Dose adjustments in case of QT prolongation should be performed per [Section 6.5.1.1](#).

A standard 12 lead ECG will be performed:

- at screening or baseline (Triplicate ECG to be collected to assess QTcF intervals)
- at Week 26 and Week 52
- at the end of treatment

